## **II. SPECIFIC AIMS**

**Specific Aim #1 (Feasibility [primary outcome], acceptability, immediate impact):** To assess the feasibility, acceptability, and immediate impact of the PP-based health behavior intervention

on optimism and happiness in a three-arm (N=75), randomized, controlled pilot trial.

*Hypothesis: The PP intervention will be feasible (the majority of participants will complete at least 7 of 12 sessions/exercises) and acceptable (mean score of at least 6 out of 10 on ratings of ease of completion and subjective helpfulness of the exercises) and will have adequate immediate impact on positive affect and optimism (post-exercise ratings of positive affect and optimism will be higher than pre-exercise ratings (measured by pre- and post- measurements on a Likert scale).*

**Specific Aim #2 (overall impact on psychological health):** to examine the intervention's overall impact on both positive (positive affect, optimism) and negative (depression, anxiety) psychological health, compared to TAU and an MI-based educational control condition.

*Hypothesis: The intervention will lead to significant pre-post increases in positive affect and optimism and significant reductions in depression and anxiety. Compared to the control conditions, the PP-based intervention will lead to greater numerical improvements in all psychological outcomes.*

**Specific Aim #3 (adherence and functional outcomes):** To examine the impact of the intervention on physical activity (steps, as measured by accelerometer; primary health behavior outcome), medication adherence, sodium intake, HF-related QoL, and generic HRQoL, compared to TAU and an MI-based educational control condition.

*Hypothesis: The intervention will lead to significant pre-post improvements in adherence and functional outcomes at follow-up and will lead to greater numerical improvements in these outcomes compared to the treatment as usual and the MI-based control condition.*

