## E. Data to be collected (See Table 1)

**Baseline Data:** Participants will complete the MOS, SSQ, SOM, LOT-R, PANAS, HADS, KCCQ, SRMA, and SF-12 in person and will receive an Actigraph accelerometer. They will be asked to begin wearing the accelerometer after their initial visit and prior to in-person visit #2 to measure their baseline physical activity.

Baseline information about enrolled participants will also be obtained from the participants, care providers, and electronic medical record as required for characterization of our population. This information will include data regarding medical history (history of coronary artery disease, acute coronary syndrome, coronary artery bypass graft, hypertension, diabetes mellitus, hyperlipidemia, body mass index, height, weight, and current smoking), current medical variables (renal function, N-terminal pro-B-type natriuretic peptide, left ventricular ejection fraction, NYHA class), medications, and sociodemographic data (age, gender,

race/ethnicity, living alone, education). This information will help us to ensure that the population we recruit is a representative population of patients suffering from HF so that the health behavior intervention we are testing is applicable to the broadest population of patients.

**Feasibility (primary study aim):** Feasibility will be measured by the number of PP sessions that were completed by participants. We will consider the intervention feasible if the majority of participants complete at least 7 of 12 exercises/sessions.

**Acceptability:** Following each PP exercise, participants will be asked to rate the ease of completion and subjective helpfulness of the exercise on a scale of 0 (very difficult/not helpful) to 10 (very easy/very helpful).

**Immediate impact:** To examine the immediate impact of the PP exercises on positive affect and optimism, participants will be asked to rate these psychological states before and after each exercise on a 10-point Likert scale (0 = not happy/optimistic, 10 = very happy/optimistic).

**Measurement of health behaviors.** We will assess three main health behaviors in this trial.

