#### Measures:

- Rates of completion of exercises (recorded by study trainer).
- Successful use of ActiGraph accelerometer.
- Patient rating of immediate outcomes on 10-point Likert scale: Ease of completion, overall utility, change in positive affect and optimism from pre- to post-exercise.

The intervention will be considered feasible if  $\geq 7$  of the 12 sessions are completed by a majority of patients. The objective assessment measures will be considered feasible if we obtain adequate physical activity data (at least 5 valid days of accelerometer wear time) in at least 80% of enrolled participants at one of the follow-up time points. The PP exercises will be considered to be acceptable if participants have mean scores of at least 6/10 on the ratings of ease of completion and subjective helpfulness across exercises. The PP exercises will be considered to have adequate impact if participants rate positive affect and optimism significantly higher post-exercise than pre-exercises across exercises (via mixed linear models).

**Aim #2** (*overall impact on psychological health*): To examine the intervention's impact on both positive (positive affect, optimism) and negative (depression, anxiety) psychological health, compared to TAU and a MI-based educational control condition.

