**D. Power analysis**

We have performed power analyses assuming 20 participants in each group. To account for potential drop outs between enrollment and randomization, we will enroll 75 participants with a goal of randomizing 60. This pilot trial is not designed to detect significant between-group differences in 12- or 24-week health behavior outcomes, but is powered to meet our primary aims of feasibility and immediate impact. For feasibility, 75-80% of subjects have completed the majority of PP exercises in our prior work, and 90% completed the majority of PP exercises in our proof-of-concept trial in patients with HF. With 20 PP participants, we will have at least 80% power to detect a difference between our expected proportion of participants completing at least 5 out of 8 PP exercises (80%) and the null hypothesis (true proportion of 50% or less) at the

two sided 0.05 level using a binomial proportion test. In a prior study, we found that PP interventions led to a moderate ( $d=.52$ ) improvement in optimism immediately post-exercise. If we assume completion of ~140 exercises from 20 subjects and a within-person correlation of 0.5 for change in pre-/post- ratings across exercises, our proposed study is powered at over 80% to detect a similar effect size improvement of optimism immediately post-exercise at the two-sided 0.05 level.

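### The power statement for the primary feasibility outcome names 5 of 8 exercises although the rule is 7 of 12, and its 0.05/80% figures belong to a binomial test that the statistical methods do not list

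*Combined protocol and SAP*

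**What the plan says.** Feasibility is the primary outcome. Section II (Aim 1 hypothesis) expects that "the majority of participants will complete at least 7 of 12 sessions/exercises". Section V.E, under Feasibility, says "We will consider the intervention feasible if the majority of participants complete at least 7 of 12 exercises/sessions". The Aim 1 measures in VI.A and B repeat the rule: at least 7 "of the 12 sessions are completed by a majority of patients".

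Section VI.D says the trial "is powered to meet our primary aims of feasibility and immediate impact". For feasibility it takes 20 PP participants and claims at least 80% power. The comparison is between the expected share of "participants completing at least 5 out of 8 PP exercises (80%) and the null hypothesis (true proportion of 50% or less". The criterion for rejecting that null is given as "two sided 0.05 level using a binomial proportion test". The supporting rates are 75-80% completing most exercises in the team's prior work, and "90% completed the majority of PP exercises in our proof-of-concept trial in patients with HF". A second calculation in the same section, for immediate impact, begins "If we assume completion of ~140 exercises from 20 subjects".

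Section VI.C plans descriptive statistics for exercise completion. It names no test and no null hypothesis for feasibility.

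**The concern.** Two things do not line up. First, VI.D's power statement names a threshold and a number of exercises that this trial does not use. Second, VI.D attaches a significance level and a power to feasibility, while V.E and VI.A and B declare feasibility on a majority and VI.C describes completion without testing it. VI.A and B do specify a significance criterion for immediate impact, so a reader cannot take one as implied for feasibility.

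Feasibility is the conclusion this pilot exists to reach. If majority means more than half of the observed participants, the 0.05 and 80% are not properties of that rule, and a result could be called feasible while remaining compatible with a true completion rate of 50%. If VI.D's test is what majority means, the analysis section omits the primary outcome's only test. The plan does not say which applies.

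**Working it through.** **Inputs.** From VI.D: n = 20 PP participants, null proportion 0.50, expected proportion 0.80, two-sided 0.05, prior rates of 75-80% and 90%. From II, V.E and VI.A and B: majority of participants, at least 7 of 12.

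**1. The label.** 8/2 = 4 and 12/2 = 6, so 5 of 8 and 7 of 12 are each the smallest strict majority of their programme. VI.D's second calculation uses 140/20 = 7 exercises per participant, which fits the 12-session programme. So 5 of 8 looks like a leftover from a shorter programme.

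**2. Reproducing the stated power.** Let X be the number of the 20 who reach the threshold, with P(X ≥ r) = Σ C(20,k) p^k (1−p)^(20−k), summed from k = r to 20. At p = 0.50:
- r = 14: 60,460/1,048,576 = 0.0577, two-sided 0.115, not significant.
- r = 15: 21,700/1,048,576 = 0.0207, two-sided 0.041, significant.

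The test therefore needs 15 of 20. At p = 0.80, P(X ≥ 15) = 0.804, so the claim of at least 80% reproduces. Normal and arcsine approximations both give 82%; a continuity-corrected one gives 73%. None of these inputs involves 5 of 8, so relabelling to 7 of 12 leaves the figure unchanged if 80% is kept.

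**3. Sensitivity to the 80%.** At 75%, the low end of VI.D's own range, P(X ≥ 15) = 0.617. At 90%, the HF proof-of-concept rate, it is 0.989.

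**4. Majority read as an observed count.** More than half of 20 is 11 or more. At p = 0.50, P(X ≥ 11) = 431,910/1,048,576 = 0.412. The last column is the difference between the two before it.

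| True proportion | Majority count, X ≥ 11 | Binomial test, X ≥ 15 | They disagree, 11 to 14 |
|---|---|---|---|
| 50% | 41.2% | 2.1% | 39.1% |
| 75% | 98.6% | 61.7% | 36.9% |
| 80% | 99.7% | 80.4% | 19.3% |
| 90% | >99.9% | 98.9% | 1.1% |

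**5. What the boundary results say.** Exact (Clopper-Pearson) 95% intervals and two-sided p-values against 50%:
- 11/20: 32% to 77%, p = 0.82
- 14/20: 46% to 88%, p = 0.115
- 15/20: 51% to 91%, p = 0.041

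The lower limit exceeds 50% exactly when the test gives an upper-side rejection, so the interval and the test carry the same message.

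**6. The second calculation.** With 7 exercises each and a within-person correlation of 0.5, the design effect is 1 + 6 × 0.5 = 4 and the effective number is 140/4 = 35. Taking d = 0.52 as standardised on the change score (an assumption), power = Φ(0.52 × √35 − 1.96) = 0.87. VI.D's claim of over 80% holds.

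**The case against.** The strongest reply is that this is one stale label with no numerical effect. The endpoint is consistent in II, V.E and VI.A and B, so nobody running the trial would score 5 of 8. VI.D states its supporting rates for completing most exercises, not for 5 of 8. As a fraction, 7/12 (58%) is less demanding than 5/8 (62.5%), and the assumed 80% lies below the 90% seen in HF patients. All of that stands. It limits the label error to a correction. It does not make the carry-over of 80% explicit, and I.B describes the earlier HF programme as 10 weeks long.

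The second reply is that VI.D's null, 50% or less, is the complement of a majority. On that reading majority refers to the true proportion, the test is the rule, and VI.C is merely incomplete. This is a fair reading and the documents do not exclude it. It still requires an edit to VI.C.

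Third, the 41% needs context. A rule of more than half passes just under half the time at a true 50% by construction, and 50% is only the edge of VI.D's null. At a true 40% the count passes about 13% of the time, and at 30% about 2%. That stands too.

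A reader might infer that 20 PP participants is unsupported, or that the plan carries a 41% false-positive rate. The documents support neither. The 80% figure reproduces, and VI.D has a second calculation behind the same 20. The 41% applies only to the count reading, at the boundary of the null.

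**Conclusion.** The point holds in a limited form. VI.D's threshold is wrong as written: it should name the 7-of-12 rule used elsewhere. The stated power is arithmetically right and carries over to 7 of 12 on the assumption that 80% is still the expected rate; at 75% it is 62%.

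The decision rule is unresolved rather than demonstrably wrong. The 0.05 and 80% describe a binomial test needing 15 of 20, which VI.C does not list. Read as an observed count, the majority rule needs only 11. The practical gap depends on true completion: results on which the two disagree occur 37% of the time at 75%, 19% at 80% and 1% at 90%. These figures assume exactly 20 PP participants in the denominator and independent outcomes. The point should be fixed, but it calls for no change to the design.

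**What to change.** **VI.D.** Replace 5 out of 8 exercises with 7 of 12 sessions. State that the 80% is assumed to carry over from the earlier programmes, and give the power at 75% (62%) beside that at 80%. Say that the 0.05 and 80% describe the binomial test (15 or more of 20), not an observed majority.

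**VI.C.** Report the proportion of PP participants completing at least 7 of 12 sessions, with its exact 95% confidence interval and the binomial test against 50% that VI.D powers. State the denominator. All participants randomized to PP is suggested, because it matches the 20 in VI.D; V.E and VI.A and B do not define it, and VIII.C ties the formal analysis to 60 people who have completed the trial.

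**V.E and VI.A and B.** The majority rule can stay as the pilot's benchmark. Whether the test should become the success criterion is for the sponsor to decide; it trades a much lower pass rate at a true 50% (2% instead of 41%) for a lower one at 75% (62% instead of 98.6%).

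**Cost.** A few sentences and a slightly less favourable power statement. Sample size and data collection do not change.

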## **VII. RISKS AND DISCOMFORTS**

### **A. Complications of surgical/non-surgical procedures**

No procedures will be conducted as part of this study

### **B. Drug side effects and toxicities**

No specific medications are being studied or administered solely for research purposes in this study.

### **C. Device complications**

No specific devices are being studied or administered solely for research purposes in this study. We are using an accelerometer and step-counter that, although not determined to be a “device,” can malfunction. The device utilized to measure physical activity should pose minimal risk. The accelerometer (ActiGraph GT3X+) used to measure activity is small, light, and without sharp edges. Immersing the device in water for a prolonged period may render it unusable but does not pose a shock risk. Participants will mail the device back after 7 days in a pre-paid envelope provided by the study team. The Omron pedometer which we will provide participants to use in self-monitoring similarly poses minimal risk, given that it has no sharp edges, no shock risk, and no other known risks.

We will provide explicit instructions regarding the use of the accelerometer and step counter to ensure safety and proper use, and to reduce inconvenience/distress associated with uncertainty about their safety or use. We will reduce technological failure by educating study participants and providing a technical help line as noted above. The scientific team (i.e., [name] or other study staff member) will liaise with participants regarding any battery problems or technical advice on the Actigraph accelerometer, step counter, and related equipment. The participant will be instructed to contact study staff by phone should a problem develop with the accelerometer during the course of the study. If there is an irresolvable problem, the participant will send the device back to the research assistant, and be provided a new one. Study staff will work directly with Actigraph or Omron technical support to resolve any device issues. A log of all technical difficulties will be maintained.

### **D. Psychosocial risks**

**Confidentiality.** As with any study, there is the risk of a breach of confidentiality; these risks will be minimized by using participant numbers rather than identifying personal data on study documents, and by using locked cabinets/offices and password-protected databases to store

personal information. Only study staff (the PI, the research assistant entering data, co-investigators delivering the intervention, and the research assistant doing follow-up assessments) will have any access to personally identifiable information about participants, and such access will be limited only to information necessary to complete study tasks.

All data regarding the objective adherence devices will be encoded only with the study participant number that is linked to personal identifying information in the study database. The devices will not be marked with any personal identifiable information, and the database that will be used to monitor accelerometer data will only contain participant numbers. The accelerometers do not record or link participants' names with their data, and accelerometer data will only be accessed from a locked Partners computer in a research team office.

We will ensure that contact with participants is confidential by using only the phone numbers and other contact information that are specifically allowed by the participants and not leaving study-related messages for participants unless expressly allowed by participants. Upon enrollment, we ask all participants if it is acceptable to leave voice messages on their phones, as well as the appropriate times to call them. We adhere to any and all patient requests regarding contact.

Partners Healthcare has an electronic system that lets study doctors know if participants are admitted to a Partners Hospital, or if a participant visits a Partners Hospital Emergency Department. This allows study doctors to know about any possible problems or side effects a participant experiences while taking part in the study.

**Informed consent process.** With regard to the consent process, we will approach/recruit participants in the hospital only after patients' treatment team members (who would not be associated with the consent process in any way) ask patients if they are interested in hearing more about an optional study. In the outpatient setting, we will only contact those participants who express interest in the study or do not opt out after receiving an opt-out letter. If an investigator is clinically caring for a potential participant, an alternate, trained study staff member will approach the patient and complete the informed consent process and all study procedures for that participant. When discussing the study, we will emphasize the study's optional nature and participants' ability to opt out/un-enroll at any time, for any reason.

**Medical & psychiatric emergencies.** As with any program which promotes an increase in physical activity, there is an inherent potential physical risk imposed (e.g., falls, worsening cardiac symptoms). For those who enroll in the program and give us permission to communicate with their clinician, we will inform the clinician of their patient's participation and offer to speak to them if they have any concerns or recommendations about setting goals related to physical activity or other health behaviors. If patients report acute medical symptoms, they will be directed to emergency medical care, and their primary medical physicians may be contacted as needed. If study staff have questions regarding medical symptoms and their urgency, [name] (co-investigator and cardiologist) and the PI will be available to consult (and call patient) as needed.

This study utilizes a questionnaire that assesses depressive symptoms (HADS), and thus, participants might disclose information about suicidal thinking or behavior. Due to this possibility, the follow-up call will be performed at a time when a psychiatrist study investigator is available to intervene as needed. If participants report suicidal ideation, study staff will complete specific suicide risk assessment questions to assess immediate risk of self-harm, and

the psychiatrist will immediately assess the situation/patient if there is either an acutely elevated risk of self-harm or if additional information is needed to clarify risk. If the patient is at imminent risk, the study psychiatrist will take all needed steps to ensure emergent evaluation, which may include ensuring evaluation in the nearest emergency room. Participants will be informed of all of these measures to ensure confidentiality—and the limits of confidentiality, such as arranging for emergent medical or psychiatric care if safety is at imminent risk—as part of the informed consent process. However given that this is a medical rather than a psychiatric population we anticipate the rate of suicidality in this population will be low.

We will ask participants to report adverse events related to study participation they may have experienced at any time throughout the study. Any adverse events will be reported to the PI and to the IRB according to Partners HRC guidelines.

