Finally, once a participant signs the consent form, the investigator will perform a focused review of the participant's medical record (including laboratory data) to again confirm that the patient has HF, and will consult with the study cardiologist in the event that there is any need for further clarification. If there is a question about the patient's medical prognosis (to assess whether the patient has a condition likely to lead to death within 6 months) the study team will consult with the patient's inpatient or outpatient team and/or the study cardiologist. Participants will be asked to sign a release form at the time of consent to allow study staff to discuss their diagnosis and aforementioned medical variables during the study.

Partners Healthcare has an electronic system that lets the participants' study doctors know if they are admitted to a Partners Hospital, or if they visit a Partners Hospital Emergency Department. We will use this system to ensure that the study doctors know about any possible problems or side effects participants experience while taking part in the study.

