### Follow Ups:

**Follow-up phone calls (Week 12 and Week 24 [post randomization]).** At Weeks 12 and 24, a member of the study staff will call participants to repeat the self-report questionnaires that were administered at baseline. These questionnaires assess state optimism (State Optimism Measure; SOM), general optimism (LOT-R), positive affect (PANAS), overall health behavior adherence (MOS), anxiety/depression (HADS), HRQoL (SF-12), cardiac symptoms and HF-related QoL (KCCQ), medication adherence (SRMA), and sodium intake (SSQ). Participants will also be asked about cardiac-related hospital readmissions and cardiac rehabilitation, and to rate their overall satisfaction with the treatment they received for their cardiac condition over the course of the study on a scale of 0 (not at all satisfied) to 10 (completely satisfied). Finally, patients will be asked about their experience in the study, including any aspects of the intervention or study procedures that could be improved, during follow-up assessment. In sum, these scales should take approximately 30-40 minutes to complete. If participants would rather complete the follow-up questionnaires in written form rather than over the phone, we will send them a paper packet at the time of the follow-up.

**Training.** [name] (PI) has substantial experience in explaining and delivering PP exercises from their studies in cardiac and psychiatric patients. The PP exercises for this trial have been identified via published literature, or directly from researchers, and modified appropriately for this population. Additional text outlining the rationale and instructions for each exercise are located in the written packets for each exercise that are provided to participants. [name] will engage in several training exercises prior to study initiation. He will review the treatment manual and our team's prior training manuals related to these exercises. He will then complete all exercises to gain experience performing and reviewing each exercise.

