**Table 1. Schedule of study events.**

	Pre-enrollment	Initial Visit	Second in Person Visit	Phone Sessions (12 weeks)	Follow-up Phone Call (Week 12)	Follow-up Phone Call (Week 24)
Cognitive screen	X					

Chart review to confirm eligibility	X					
Assessment of inclusion criteria (MOS, NYHA class)	X					
Chart review for baseline characteristics		X				
Randomization to PP or Control Condition			X			
Weekly intervention exercises*			X	X		
Exercise ratings			X	X		
Self-report measures (SSQ, SRMA, MOS, LOT-R, PANAS, HADS, KCCQ, SF-12, SOM)		X			X	X
Objective adherence data (ActiGraph step counter)		X			X	X
Satisfaction with Care					X	X
Hospital Readmissions					X	X

\*Type of exercise assigned will depend on whether participant is in PP-MI or control condition

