### **D. Adverse event reporting guidelines**

We will follow all PHRC guidelines with respect to reporting unanticipated problems, including adverse events. Specifically, when a serious or nonserious adverse event occurs, the PI will review the event to determine if it was possibly or definitely related to participation in the research. For all unanticipated problems and adverse events deemed related or possibly related to

the research, we will complete and submit an Other Event report through Insight/eIRB as soon as possible and within 5 working days/7 calendar days (as defined in the March 2014 Reporting Unanticipated Problems Including Adverse Events report). At Continuing Review, we will provide a summary of all unanticipated problems as per PHRC protocol. Finally, if there are unanticipated problems, especially if serious or recurrent, the PI ([name]) will amend the protocol if it is deemed necessary to protect the safety and welfare of the participants.

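### Participants are asked only for study-related adverse events and no question covers falls, so an unattributed event handled outside Partners has no systematic route to the PI or DSMB

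*Combined protocol and SAP*

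**What the plan says.** The plan describes event collection in several places.

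- **Request to participants (VII.D, Medical & psychiatric emergencies):** "We will ask participants to report adverse events related to study participation they may have experienced at any time throughout the study". No timing, wording or checklist is given. The next sentence deals with onward reporting: "Any adverse events will be reported to the PI and to the IRB according to Partners HRC guidelines".
- **Named risks (same section):** for a programme that promotes activity, "there is an inherent potential physical risk imposed (e.g., falls, worsening cardiac symptoms".
- **Who judges relatedness (VIII.D):** "when a serious or nonserious adverse event occurs, the PI will review the event to determine if it was possibly or definitely related to participation".
- **Structured event question (V.A, Follow Ups, weeks 12 and 24):** "Participants will also be asked about cardiac-related hospital readmissions and cardiac rehabilitation". The corresponding row of Table 1 reads "Hospital Readmissions", with no cardiac restriction. Table 1 has no adverse event row.
- **Electronic alert (IV.B and VII.D):** study doctors learn of admissions to, and emergency visits at, Partners hospitals. Section IV.B states the purpose: "We will use this system to ensure that the study doctors know about any possible problems or side effects participants experience". There is no limit by cause or by arm.
- **Contact schedule (V.A):** PP and MI participants have weekly trainer calls. TAU participants have no intervention after the randomization visit and are next seen at the 12-week follow-up.
- **Use of the data (VIII.B):** adverse event information is reviewed to decide whether the study goes on unchanged, is modified or stops. The DSMB meets every four months to monitor patient safety.

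**The concern.** The request in VII.D and the rule in VIII.D do not fit together. If the PI is to decide whether an event is related, the PI has to hear of it first. A request limited to related events hands the first decision to the participant, who may not connect a fall on an ordinary walk with a programme that encourages walking. The sentence sending any adverse event to the PI does not repair this, because staff can forward only what they have been told.

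Falls are the clearest case. The protocol names them as a physical risk, yet neither the follow-up questionnaires nor Table 1 asks about them.

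Opportunity to mention an event also differs by arm. Trainers speak to PP and MI participants weekly, and nobody is scheduled to speak to TAU participants before week 12. More recorded events in PP or MI than in TAU could reflect more conversations rather than more harm, and a quiet record could reflect the narrow question. The PI and the DSMB would be reviewing safety on that record.

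**Working it through.** The plan states no figure on this point, so there is none to reproduce. The check traces each route by which an event can reach the PI and then counts scheduled contacts.

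**Routes to the PI**

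| Route | Covers | Does not cover |
|---|---|---|
| Request to participants (VII.D) | Events the participant regards as study-related | Events not so regarded |
| Readmission question, weeks 12 and 24 (V.A text) | Cardiac-related readmissions | Non-cardiac admissions; anything without admission |
| Readmission row (Table 1) | Readmissions, no stated limit | Anything without admission |
| Electronic alert (IV.B, VII.D) | Any-cause admission or emergency visit at a Partners hospital, all arms | Outside hospitals; events managed at home |
| Spontaneous report of acute symptoms (VII.D) | What the participant volunteers | What is not volunteered |
| KCCQ symptom subset (V.E, Table 1) | HF symptom score at baseline and weeks 12 and 24, all arms | Events between assessments; falls |

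Take a fall that the participant does not attribute to the study:

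1. If it leads to a Partners admission or emergency visit, the alert brings it to the study doctors.
2. If it leads to admission elsewhere, the follow-up text does not ask about it because it is not cardiac. Table 1, read literally, would. The two passages disagree.
3. If it is managed at home, or at an outside emergency department without admission, no solicited item or alert covers it. It is known only if the participant happens to mention it.

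**Scheduled contacts after the randomization visit and before the week-12 assessment (session lists in V.A)**

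- PP: session 1 is at the visit. Sessions 2 to 12 are 11 calls, and the wrap-up adds 1: 11 + 1 = 12.
- MI: the first of 13 sessions is assigned at the visit. Sessions 2 to 13 are 12 calls.
- TAU: 0.

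With the planned 20 per arm (VI.D), that is 20 × 12 = 240 in PP, 20 × 12 = 240 in MI and 20 × 0 = 0 in TAU. Adding the two follow-up assessments gives 12 + 2 = 14, 12 + 2 = 14 and 0 + 2 = 2 contacts per participant through week 24. The plan does not say that adverse events are asked about on weekly calls, so these are opportunities to volunteer an event and not planned safety assessments.

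**What equal collection could show**

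The documents give no fall rate, so two pairs of rates are assumed for illustration. With 20 per arm and Fisher's exact test at two-sided 0.05, power is about 7% for 10% against 20%, and about 19% for 20% against 40%.

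**The case against.** Much of the plan does protect against missed events, and a reader might infer more from the gap than the documents support.

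- **That unattributed events never reach the PI.** Not supported. The alert covers any-cause Partners admissions and emergency visits in every arm. Participants come from MGH inpatient units, the MGH Heart Center and MGH-affiliated primary care, so Partners is a likely place of care. VIII.D covers serious and nonserious events alike, and VIII.C has adverse events discussed weekly.
- **That both named risks go unmeasured.** Not supported for worsening cardiac symptoms. The KCCQ symptom subset is given identically in all arms at baseline and at weeks 12 and 24, with no relatedness filter. It is a score at fixed times and does not record events in between. Falls have no counterpart.
- **That only cardiac readmissions are recorded.** The follow-up text says so, but Table 1 does not. The documents support an inconsistency to be reconciled, not the narrow reading alone.
- **That every between-arm count is distorted by contact.** PP and MI have matching schedules. The imbalance applies only against TAU, where absence of interim contact is part of the condition.
- **That the trial fails to answer a safety question it set itself.** It is a feasibility pilot with a goal of 60 randomized and no planned between-arm safety comparison. At 20 per arm, equal collection would not make such a comparison informative.

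What stands after this is the related-only request, the missing question on falls, the mismatch between text and table, and the unequal chance to report against TAU.

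**Conclusion.** The point holds in a limited form. An event that the participant does not link to the study, and that leads to no Partners admission or emergency visit, has no systematic route to the PI or the DSMB. The plain example is a fall managed at home. A fall treated at an outside hospital is in the same position, except that an admission there would be picked up if the Table 1 row is taken at face value.

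Before week 12 the scheduled opportunities to volunteer such an event are about 12 per participant in PP, 12 in MI and 0 in TAU. Recorded counts in PP or MI against TAU are therefore hard to interpret, while PP against MI is balanced.

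The number of events that would be lost cannot be estimated, because the documents give neither a fall rate nor the share of care received outside Partners. The conclusion assumes that staff follow VII.D as written and that the weekly calls carry no standard adverse event question, since none is described. It is a worthwhile, inexpensive improvement to safety data and does not affect the primary feasibility aim.

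**What to change.** Change three places so that they agree.

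1. **VII.D:** remove the restriction to study-related events from the request to participants. Leave relatedness to the PI under VIII.D.
2. **V.A, Follow Ups:** at weeks 12 and 24, ask all three arms the same short questions about the period since the last assessment, whatever the perceived cause: any hospital admission or emergency visit (any cause, any hospital), any fall, and any other adverse event. A separate cardiac symptom question is not needed for scoring, since the KCCQ is already given.
3. **Table 1:** reconcile the readmission row with the text on the any-cause, any-hospital basis, and add a row for the adverse event and fall questions.

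State that events will be described by arm from this common question set, with events volunteered on weekly calls listed separately.

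The cost is protocol wording, one added table row, a few more minutes on calls already planned, and more unrelated events to log and review.
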